2.1 Study Rationale

Small Cell Lung Cancer (SCLC), accounting for 10% to 15% of lung cancer (Rudin et al, 2015), is an aggressive lung cancer subtype with neuroendocrine differentiation and strongly associated with smoking (Koinis et al, 2016). Due to its predominantly central location and propensity to metastasize early, it is seldom amenable to surgery. Although small cell lung cancer is exquisitely sensitive to first-line chemotherapy (approximately 60 to 70% response rates) and to radiation, most patients eventually die of recurrent disease. About 1 of 3 of SCLC patients present with LS disease, which is amenable to “curative-intent” treatment with combination chemo-radiation. Unfortunately, even in this setting, long-term remission is achieved in only 20% to 25%; the remainder relapsing with progressive disease (Elegbede et al, 2020).

The majority (2 of 3) of SCLC patients present with more advanced ES disease. Extensive stage (ES) SCLC (ES-SCLC) remains a grievous diagnosis with high unmet medical need. Despite initial response to chemotherapy, patients invariably experience disease progression and develop resistance to second-line and subsequent therapies. Response to second-line and subsequent therapies is limited, and patients die as a result of disease at a median time of 10 to 12 months from diagnosis (Rudin et al, 2015). Recent addition of PD-(L)1 inhibitors to the **standard of care** (SOC) in ES disease has prolonged mOS from 10 to about 12 months (Liu X et al, 2022) but 5-year survival in these patients remains extremely low at < 3% (Wang H et al, 2020).

Therapeutic options after first-line treatment for patients with progressive or recurrent small cell lung cancer are very limited. Progression on relapse is often rapid and consequently, mOS after progression is a dismal 10 months. For those with a CFI of more than 6 months, a rechallenge with the original platin based doublet can be offered. For the majority with a shorter CFI or poorer PS, single agent topotecan is widely approved; however, it is associated with significant toxicity making it an unpopular choice. Lurbinectedin, a novel cytotoxic agent, offers a second option after receiving accelerated FDA approval for this indication and has seen significant uptake in the US, and recently in other countries as well. Several other drugs such as irinotecan, paclitaxel, or combination regimens such as cyclophosphamide, adriamycin, and vincristine (CAV; all unapproved in this setting) are often used. This echoes the limited efficacy and high toxicity seen when treating the second line SCLC patient population reflecting a broad dissatisfaction with current options. Clearly, with limited second-line

options and no approved therapy in the third-line setting, relapsed small cell lung cancer represents an acute area of unmet clinical need for most small cell lung cancer patients.

Delta-like ligand 3 (DLL3) is a non-canonical Notch ligand found intra-cellularly (localized in the Golgi apparatus) in normal tissues (Geffers et al, 2007). Delta-like ligand 3 is upregulated and aberrantly expressed on the cell surface in most SCLC tumors, making it a compelling target for T cell-based therapies (Saunders et al, 2015). In a diverse panel of normal tissues, a low level of staining with a cytoplasmic pattern was only detected in the brain, pituitary, and pancreatic islets (Study 123377), suggesting the potential for a DLL3-targeting therapy to be tumor specific in SCLC.

Tarlatamab (International Nonproprietary Name [INN]; AMG 757) is a novel half-life extended (HLE) bispecific T cell engager (BiTE®) molecule designed to direct T effector cells toward DLL3-expressing cells, with a tandem scFc moiety for extended half-life. The pharmacological effect of tarlatamab is mediated by specific redirection of previously primed cytotoxic **cluster of differentiation (CD)3⁺** T lymphocytes to kill DLL3-expressing cells.

Tarlatamab has demonstrated durable antitumor activity in subjects with ES-SCLC in a phase 2 (Study 20200491) and phase 1 study (Study 20160323) with a favorable benefit/risk profile. Please refer to the Investigator's Brochure for the most current efficacy and safety data across the tarlatamab program.

The aim of Study 20210004 is to evaluate efficacy and safety of tarlatamab compared with SOC therapy in subjects with relapsed SCLC who have progressed following 1 platinum-based regimen. The study consists of a 21-day screening period, a treatment period when subjects will be randomized to receive tarlatamab or SOC therapy (lurbinectedin or topotecan in US, Canada, Australia, Singapore, Korea; amrubicin in Japan; topotecan in all countries except Japan), an SFU visit, and an LTFU period.

2.2 Background

2.2.1 Disease

Small cell lung cancer, accounting for 10% to 15% of lung cancer (Rudin et al, 2015), is an aggressive lung cancer subtype with neuroendocrine differentiation and strongly associated with smoking (Koinis et al, 2016). It displays a distinct natural history characterized by a high growth fraction, rapid doubling time and early establishment of widespread metastatic lesions (Gustafsson et al, 2008). While 30% of patients present with disease confined to 1 hemithorax (LS), most cases have disease not encompassed

by 1 radiotherapy field (ES). Small cell lung cancer is exquisitely sensitive to first-line chemotherapy (approximately 60% to 70% response rates) and to radiation which is in stark contrast to resistance to second-line and subsequent therapies after disease recurrence (Byers and Rudin, 2015). Patients with ES-SCLC develop drug resistance and die as a result of disease at a median time of 10 to 12 months from diagnosis (Rudin et al, 2015). For patients with SCLC, first-line treatment is platinum-based chemotherapy. Most patients in the US receive platinum-etoposide (EP) chemotherapy (with either carboplatin or cisplatin), and some patients receive platinum-irinotecan as an alternative, especially outside the US. With limited second-line options and no approved therapy in the third-line setting, relapsed SCLC represents an area of acute unmet need.

2.2.2 Amgen Investigational Product Background: Tarlatamab

BiTE® molecules have been designed to direct T effector memory cells towards target cells. The proximity induced by the BiTE® triggers target cell specific cytotoxicity which closely resembles standard cytotoxic T lymphocyte activation.

Tarlatamab is an HLE BiTE® molecule combining the binding specificities for DLL3 and CD3 genetically fused to the N-terminus of immunoglobulin G (IgG) scFv region and is being developed with the intent to treat patients with SCLC. The anti-tumor activity of tarlatamab requires the simultaneous binding to both target cells and T cells. The pharmacological effect of tarlatamab is mediated by specific redirection of previously primed cytotoxic CD3⁺ T lymphocytes to kill DLL3⁺ cells.

The pivotal phase 2 study of tarlatamab in patients with relapsed SCLC after 2 lines of prior therapy has confirmed durable efficacy and favorable benefit/risk profile (Study 20200491). Based on a pre-specified interim analysis (IA) in part 1 of the phase 2 Study 20200491 the regimen using 10 mg target dose with a 1 mg step-dose was selected as the monotherapy recommended phase 2 dose (RP2D) regimen to balance the efficacy/safety of tarlatamab and to be further evaluated in part 2 and part 3 of the phase 2 Study 20200491, and any subsequent studies for tarlatamab. The primary analysis for the phase 2 Study 20200491 reinforced the selection of 10 mg target dose for tarlatamab studies.

A detailed description of the chemistry, pharmacology, efficacy, and safety of tarlatamab in all ongoing and completed clinical trials is provided in the Investigator's Brochure.

2.3 Benefit/Risk Assessment

Delta-like ligand 3 is a promising target for the development of a T cell-directed therapy due to the difference in expression levels between SCLC cells and normal tissues and the localization of DLL3 in the cytoplasm and cell membranes in tumor cells compared to localization that is restricted to the cytoplasm in normal tissues. Tarlatamab showed high activity in recruiting T cells against DLL3-expressing SCLC cell lines in vitro and significantly inhibited tumor growth in systemically treated tumor-bearing mice.

Tarlatamab has demonstrated durable antitumor activity in subjects with ES-SCLC in a phase 2 (Study 20200491) and phase 1 study (Study 20160323) with a favorable benefit/risk profile. Please refer to the Investigator's Brochure for the most current efficacy and safety data across the tarlatamab program.

Key Safety Information

Based on experience with tarlatamab in ongoing clinical studies, the key safety information for tarlatamab includes the adverse drug reactions of cytokine release syndrome (CRS), immune effector cell associated neurotoxicity syndrome (ICANS), and neutropenia. Pituitary dysfunction, other neurologic events, and tumor lysis syndrome (TLS) are additional potential safety concerns of tarlatamab and are based on the biological mechanism of action, experience with other BiTE molecules, and/or the potential for on-target, off-tumor effect. Please refer to the Investigator's Brochure for complete information.

Refer to Section [6.2.2](#) and [Table 6-2](#) for detailed management recommendation.

Given the evidence provided above, and with the mitigations and safety monitoring built into the protocol, the potential benefits to the patient are believed to outweigh the risks and potential safety concerns.

Amgen closely monitors the coronavirus disease 2019 (COVID-19) pandemic around the world. As part of this effort, Amgen performs a rigorous assessment, considering the study design, patient safety, public health risk, benefit-risk assessment, as well as the burden on country healthcare systems. Decisions are made on a study-by-study and country-by-country basis to minimize risk to patients and avoid undue burden on healthcare facilities.

The above benefit risk assessment supports the conduct of this clinical trial. Refer to the Investigator's Brochure for additional information related to risk assessment.

3. Objective(s) and Endpoint(s)

Objectives	Endpoints
Primary	

 To compare the efficacy of tarlatamab with standard of care (SOC) on prolonging overall survival (OS) 	
 OS, defined as time from randomization until death from any cause
Attributes	

 Target Population Primary Endpoint Summary Measures Intercurrent Events and Strategies 	
Primary Estimand
 
 Subjects with relapsed small cell lung cancer after platinum-based first-line chemotherapy OS Hazard ratio (HR) Start of new anti-cancer therapy OS will be estimated regardless of subsequent anti-cancer therapy (treatment policy strategy)
Primary Estimand Description	

 HR of OS between tarlatamab and SOC, for subjects with relapsed small cell lung cancer after platinum-based first-line chemotherapy, regardless of subsequent anti-cancer therapy (treatment policy strategy). 	
Key Secondary - PFS	

 Compare the efficacy of tarlatamab with SOC as assessed by progression free survival (PFS) based on investigator assessment per Response Evaluation Criteria in Solid Tumors Version 1.1 (RECIST 1.1) 	
 PFS, defined as time from randomization until disease progression or death from any cause, whichever occurs first for all subjects. Progression will be based on investigator assessment of disease response per RECIST 1.1
Attributes	

 Target Population Key Secondary Endpoint Summary Measures Intercurrent Events and Strategies 	
Key Secondary Estimand: PFS
 
 Subjects with relapsed small cell lung cancer after platinum-based first-line chemotherapy PFS HR Start of new anti-cancer therapy PFS will be censored at the last evaluable post-baseline tumor assessment prior to start of new anti-cancer therapy (hypothetical strategy)
Key Secondary Estimand Description - PFS	

 HR of PFS between tarlatamab and SOC, for subjects with relapsed small cell lung cancer after platinum-based first-line chemotherapy, prior to start of new anti-cancer therapy (hypothetical strategy) 	

Key Secondary - PRO	

 Compare the treatment effect of tarlatamab with SOC on Patient-reported disease-related symptoms, Physical Function, and Quality of Life 	
 Change from Baseline assessed 6-weekly over time to 18 weeks 
Chest Pain as measured by European Organization for Research and Treatment of Cancer Quality of Life Questionnaire Lung Cancer 13 (EORTC-QLQ-LC13)
 
Cough as measured by EORTC-QLQ-LC13
 
Dyspnea as measured by EORTC Cancer Quality of Life Questionnaire 30 (EORTC-QLQ-C30) and EORTC-QLQ-LC13
 
Physical Function as measured by EORTC-QLQ-C30
 
Global Health Status of life as measured by EORTC-QLQ-C30

Attributes	Key Secondary Estimand: PRO

 Target Population 	
 Subjects with relapsed small cell lung cancer after platinum-based first-line chemotherapy

 Key Secondary Endpoint 	
 Patient-reported outcome (PRO)

 Summary Measures 	
 Change from Baseline assessed 6-weekly over time to 18 weeks

 Intercurrent Events and Strategies 	
 Discontinuation of treatment PRO measurements before or on discontinuation of treatment will be used to estimate treatment effect (hypothetical strategy)
Key Secondary Estimand Description – PRO	

 Change from Baseline assessed 6-weekly over time to 18 weeks in PRO endpoints between tarlatamab and SOC, for subjects with relapsed small cell lung cancer after platinum-based first-line chemotherapy. PRO measurements before or on discontinuation of treatment will be used to estimate treatment effect (hypothetical strategy) 	
Secondary	

 Compare the efficacy of tarlatamab with SOC as assessed by PFS at 1 year from randomization, objective response (OR), disease control (DC), and duration of response (DOR) based on investigator assessment per RECIST 1.1, and OS at 1 year, 2 years, and 3 years from randomization 	
 OR, defined as best overall response (BOR) of complete response (CR) + partial response (PR) DC, defined as CR + PR + stable disease (SD) DOR, defined as the time from the first documentation of OR until the first documentation of disease progression or death due to any cause, whichever occurs first. Only subjects who have achieved OR will be evaluated for DOR PFS rate at 1 year from randomization

	
 OS rate at 1 year, 2 years, and 3 years from randomization

 Compare the safety and tolerability of tarlatamab with SOC 	
 Incidence of treatment-emergent adverse events including grade ≥ 3 treatment-emergent adverse events, serious treatment-emergent adverse events, treatment-emergent adverse events leading to treatment discontinuation, fatal treatment-emergent adverse events, and treatment-related adverse events

 Characterize the pharmacokinetics (PK) of tarlatamab 	
 Serum concentrations of tarlatamab

 Evaluate the immunogenicity of tarlatamab 	
 Incidence of anti-tarlatamab antibody formation

 Compare the treatment effect of tarlatamab with SOC on remaining PRO measures 	
 Time to deterioration (TTD) for symptom scales 
Chest Pain as measured by EORTC-QLQ-LC13
 
Cough as measured by EORTC-QLQ-LC13
 
Dyspnea as measured by EORTC-QLQ-C30 and EORTC-QLQ-LC13
 
 Change from Baseline assessed 6-weekly over time to 18 weeks 
Pain as measured by Brief Pain Inventory - Short Form (BPI-SF)
 
Remaining domains for QLQ-C30 and QLQ-LC13
 
Patient Global Impression of Severity (PGIS) (overall and for each symptom included in key secondary)
 
Patient Global Impression of Change (PGIC) (overall and for each symptom included in key secondary)
 
 Summary scores at each assessment and change from baseline of visual analogue scale (VAS) score as measured by 5-level EuroQol-5 Dimension (EQ5D-5L)

 Evaluate the severity and impact of symptomatic toxicity of tarlatamab and SOC 	
 Comparison of responses to selected questions from the PRO-CTCAE item bank A single question from FACT-G on symptom bother

4. Study Design

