Once consented to the study, subjects will undergo protocol-required screening assessments to confirm all eligibility requirements of the study have been met. Subjects must have measurable lesions as defined per RECIST 1.1 within the 21-day screening period and must have adequate organ function.

For a full list of eligibility criteria, please refer to Section 5.1 to Section 5.2.

Treatments

- **Amgen Investigational Product:** Tarlatamab
- **Non-Amgen Investigational Product:** Standard of care chemotherapy (lurbinectedin [US, Canada, Australia, Singapore, and Korea], topotecan [all countries, except Japan], or amrubicin [Japan])
- **Noninvestigational Product:** In some regions, the investigational product(s) and/or noninvestigational product(s)/auxiliary medicinal product(s) administered as support or escape medication for preventative, diagnostic, or therapeutic reasons, or as SOC for a given diagnosis, may be considered noninvestigational medicinal products

Study treatment will be administered as follows:

- Tarlatamab will be administered as a 60-minute intravenous (IV) infusion with a step dose (1 mg tarlatamab) on cycle 1 day 1 (C1D1) followed by 10 mg target dose on cycle 1 day 8 (C1D8) and C1D15, and every 2 weeks (Q2W) thereafter (ie, C2+ D1/D15 dosing) in a 28-day cycle.
 - Monitoring - cycle 1: Monitoring required for 6 to 8 hours post-infusion at C1D1 and C1D8.

- Cohabitant (caregiver) support for 24 hours post-infusion and the ability to stay within 1 hour of a hospital for 24 hours is required.
- Counseling the subject and caregiver on signs and symptoms of CRS and ICANS by a health care provider is required prior to discharge.
- Subjects return to site on cycle 1 day 2 and cycle 1 day 9 for vital signs and physical examination.
- At subsequent visits, additional monitoring may be required post-infusion. Refer to Section 6.1.1 (Table 6-1).
- o Pre- and post-infusion medication requirements:
 - Dexamethasone: 8 mg IV (or equivalent) will be administered within 1 hour prior to tarlatamab infusion on C1D1 and C1D8
 - IV hydration: 1 L normal saline over 2 to 4 hours following tarlatamab doses on C1D1 and C1D8
- Standard of care (21-day cycle): Standard of care will be administered as follows in a 21-day cycle.
 - o Lurbinectedin (US, Canada, Australia, Singapore, and Korea) will be administered as 3.2 mg/m² IV on day 1 every 3 weeks

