 - o Topotecan (all countries, except Japan and China) will be administered as IV at 1.5 mg/m² or oral at 2.3 mg/m²/day on days 1, 2, 3, 4, and 5 every 3 weeks
 - o Topotecan (China mainland [China mainland in this clinical study shall be referred as "China"] will be administered as IV at 1.2 mg/m² or other locally approved dose or oral at 2.3 mg/m²/day on days 1, 2, 3, 4, and 5 every 3 weeks
 - o Amrubicin (Japan) will be administered as 40 mg/m² IV on days 1 to 3 every 3 weeks

For full understanding of the treatment groups, see the Study Schema (Section 1.2).

Statistical Considerations

Approximately █ subjects per arm, total of approximately █ subjects will be enrolled.

The hypotheses of the primary efficacy endpoint overall survival (OS), key secondary efficacy endpoint progression free survival (PFS), and key secondary patient-reported outcome (PRO) endpoints will be tested. The OS endpoint will be tested with █ overall type I error (alpha) of █. If OS is significant, the key secondary efficacy endpoints of PFS and selected PRO endpoints can be tested sequentially in this order.

If both hypotheses of OS and PFS are rejected, the next 3 endpoints of change from baseline over time to week █ in 3 lung cancer symptoms including chest pain, cough, and dyspnea will be tested using Holm's procedure. Hypotheses are rejected sequentially based on the smallest p-value.

If all 3 hypotheses listed above are rejected, the next 2 PRO endpoints will be tested using the Holm's procedure, including change from baseline over time to week █ in physical functioning and global health status. Hypotheses are rejected sequentially based on the smallest p-value.

Overall Survival (OS):

A total of █ OS events will provide █ % power to demonstrate superiority at an alternative HR of █ with log-rank test using █ overall type I error of █ in a group sequential design with █ interim analysis and █ primary OS analysis. Under exponential assumption, assuming that the SOC mOS is █ months (Spigel et al, 2021), a HR of █ reflects a █-month improvement in OS of the tarlatamab arm over SOC arm. The interim analysis is triggered at the time when █ % (█ OS events occur. The dropout rate is anticipated to be █ % per year assuming an exponential distribution.

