1.2 Study Schema

Figure 1-1. Study Schema

AUS = Australia; CAN = Canada; CF1 = chemotherapy-free interval; DC = disease control; DOR = duration of response; IA = interim analysis; KOR = Korea; N = number of subjects; OR = objective response; OS = overall survival; PA = primary analysis; PD-L1 = programmed cell death (ligand) 1; PFS = progression free survival; PRO = patient-reported outcomes; SFU = safety follow-up; SGP = Singapore; SOC = standard of care; USA = United States of America^a

^a Stratified by: prior anti-PD-(L)1 exposure, CF1, presence (previous or current) of brain metastases (yes or no), and SOC.

^b Subjects will receive study treatment until disease progression, unacceptable toxicity, withdrawal of consent, death, or end of study as determined by the sponsor (whichever occurs first).

^c End of Treatment visit will occur at the time the decision is made to discontinue study treatment and prior to start of new anti-cancer treatment.

^d Safety Follow-up visit will occur approximately **60** (±5) days after last study treatment administration.

^e Long-term Follow-up for survival approximately every 12 weeks (± 14 days) after the SFU visit, or last imaging visit, whichever is later, for up to 3 years from last subject enrolled, or 1 year from the subject's last dose of study treatment, whichever is later.

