Table 1-3. Standard of Care Schedule of Activities

Procedure ^a	SCR	Study Treatment (21-day [+3 day] Cycles)						Q6W ^g	As Clinically Indicated	EOT	SFU ^b	LTFU ^c	NOTES
Day	-21 to 0	1	2	3	4	5	8	15					
PATIENT-REPORTED OUTCOMES AND HEALTH ECONOMIC ASSESSMENTS													
EORTC-QLQ-C30	X	X				[X]	[X]	X	X	X	X	X	Completed before study specific procedures and before subject is informed of their disease status. PROs are to be collected regardless of dosing delay.
EORTC-QLQ-LC13	X	(X)				X	[X]	X	X	X	X	X	
PRO-CTCAE	X	X				[X]	[X]	X	X	X	X	X	
GP5 From FACT-G	X	X				[X]	[X]	X	X	X	X	X	
EQ5D-5L	X	(X)				X	X	X	X	X	X	X	(X): In addition to EORTC-QLQ-C30, PRO-CTCAE, and GP5 from FACT-G, collect all other PROs at cycle 1 day 1 and every 6 weeks thereafter.
PGIS	X	(X)				X	X	X	X	X	X	X	[X]: Collect weekly for first 12 weeks and then every 6 weeks thereafter.
PGIC	(X)	(X)				X	X	X	X	X	X	X	
BPI-SF (Pain)	X	(X)				X	X	X	X	X	X	X	
STUDY TREATMENTS													
Lurbinectedin administration		X											USA, Canada, Australia, Singapore, and Korea
Topotecan administration		X	X	X	X								All countries, except Japan. Additional dosing information will be collected through a web-based diary when subjects self-administer oral topotecan at home.
Amrubicin administration		X	X	X									Japan

BPI-SF = Brief Pain Inventory - Short Form; C1D1 = cycle 1 day 1; C1D8 = cycle 1 day 8; C4D1 = cycle 4 day 1; CR = complete response; CT = computed tomography; CTCAE = Common Terminology Criteria for Adverse Events; [REDACTED] ; D1 = day 1; EC = Ethics Committee; ECG = electrocardiogram; ECHO = echocardiogram; ECOG PS = Eastern Cooperative Oncology Group Performance Status; EORTC-QLQ = European Organization for Research and Treatment of Cancer Quality of life Questionnaire; EOT = end of treatment; EQ5D-5L = 5-level EuroQol – 5-Dimension; [REDACTED] ; FACT-G = Functional Assessment of Cancer Therapy – General; FFPE = formalin-fixed, paraffin-embedded; FSH = follicle-stimulating hormone; F14 = free T4; HIV = human immunodeficiency virus; IECC = independent ethics committee; IGF-1 = insulin like growth factor 1; IHC = immunohistochemistry; IRB = Institutional Review Board; IV = intravenous; LC13 = lung cancer 13; LDH = lactate dehydrogenase; LH = luteinizing hormone; LSE = last subject enrolled; LTFU = long-term follow-up; MRI = magnetic resonance imaging; MUGA scan = multigated acquisition scan; NYHA = New York Heart

Page 6 of 6

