Association; PD = progressive disease; PGIC = Patient Global Impression of Change; PGIS = Patient Global Impression of Severity; PK = pharmacokinetic; PO = per oral; PR = partial response; PRO-CTCAE = Patient-Reported Outcomes Version of the Common Terminology Criteria for Adverse Events; PROs = Patient Reported Outcomes; Q6W = every 6 weeks; SCLC = small cell lung cancer; SCR = screening; SFU = safety follow-up; SoA = schedule of activities; SOC = standard of care; TSH = thyroid-stimulating hormone; USA = United States of America.

^a All procedures and assessments on dosing days are to be completed prior to study drug administration unless otherwise noted in the SoA.

^b Safety Follow-up visit will occur approximately **60** (± 5) days after last dose of study treatment.

^c Long-term Follow-up will occur every 12 weeks (± 14 days) from the SFU visit or last imaging visit, whichever is later for up to 3 years after LSE, or 1 year from the subject's last dose of study treatment, whichever is later. **Ad hoc vital status (survival status) collection may be required to support key study analysis.**

^d **Highly sensitive serum pregnancy test (for subjects of childbearing potential) at screening; serum or urine pregnancy test on day 1 of every cycle while receiving investigational product and then monthly following EOT until 60 days from the last tarlatamab dose.** Additional on-treatment pregnancy testing may be performed at the investigator's discretion if there is suspicion that a female subject is pregnant or per local laws and regulations.

^e If screening local labs are obtained within 48 hours prior to C1D1 dose, pre-infusion C1D1 samples do not have to be repeated. **Cycle 2 and beyond, local labs may be obtained within 48 hours prior to dose.** Results must be reviewed prior to study drug administration.

^f TSH and FT4, lipase and amylase if obtained within 72 hours prior to C1D1 dose, pre-infusion C1D1 samples do not have to be repeated. At subsequent visits, local labs may be obtained up to 72 hours prior to dose. Results must be reviewed prior to study drug administration.

^g Q6W (every 6 weeks [± 7 days]) from C1D1; except where noted in the SoA for [REDACTED]

2. Introduction

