Last Dose Administered	Duration of Delay from the Last Dose Administered	Action
Step dose (1 mg)	≤ 14 days	Proceed with tarlatamab target dose and then continue treatment regimen
	> 14 days	Repeat tarlatamab step dose per cycle 1 guidelines, including pre-medication and monitoring requirements (Refer to Table 6-1).
First target dose (10 mg)	≤ 21 days	Proceed with tarlatamab target dose and then continue treatment Q2W
	> 21 days	Repeat tarlatamab step dose schedule per cycle 1 guidelines, including pre-medication and monitoring requirements (Refer to Table 6-1).
Any subsequent target dose (10 mg)	≤ 28 days	Proceed with tarlatamab target dose and then continue treatment Q2W
	> 28 days	Repeat tarlatamab step dose per cycle 1 guidelines, including pre-medication and monitoring requirements (Refer to Table 6-1).

Q2W = every 2 weeks.

6.2.2.2 Non-Amgen Noninvestigational Product/Auxiliary Medicinal Product (SOC Chemotherapy) - Lurbinectedin, Topotecan, or Amrubicin

The reason for lurbinectedin, topotecan, or amrubicin delay or discontinuation is to be recorded on each subject's CRF. Refer to the regional prescribing information or institutional guidelines (if not addressed in prescribing information) for recommended dose modifications.

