8.1.3 End of Treatment

Upon permanent discontinuation from study treatment for any reason, an End of Treatment (EOT) visit will be performed as soon as possible (within 14 days) after last dose and prior to start of subsequent anti-cancer therapy. **If a subject is unable to attend the EOT visit, the subject at minimum should be followed via telephone, clinic visit, or chart review to assess for survival and the commencement of subsequent cancer therapy.**

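### Does the undated 'discontinuation' in the PRO estimand, with two different End of Treatment timings, bias the key secondary PRO comparisons?

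*Protocol*

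**What the plan says.** The PRO estimand in protocol Section 3 (repeated in the synopsis) treats stopping of treatment as the intercurrent event: "PRO measurements before or on discontinuation of treatment will be used to estimate treatment effect (hypothetical strategy". No calendar date is attached to discontinuation.

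The EOT visit is timed in two places. Footnote c of the study schema (Section 1.2): "End of Treatment visit will occur at the time the decision is made to discontinue study treatment". Section 8.1.3: "visit will be performed as soon as possible (within 14 days) after last dose". Both apply to all subjects.

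The analysis uses 6-weekly scores to week 18. The footnotes to Tables 1-2 and 1-3 count these visits "Q6W (every 6 weeks [± 7 days]) from C1D1". Tarlatamab is given on days 1, 8 and 15, then "every 2 weeks (Q2W) thereafter (ie, C2+ D1/D15 dosing) in a 28-day cycle". The comparators run in 21-day cycles: topotecan "on days 1, 2, 3, 4, and 5 every 3 weeks", amrubicin on days 1 to 3, lurbinectedin on day 1. The PRO notes in Table 1-3 read: "Completed before study specific procedures and before subject is informed of their disease status. PROs are to be collected regardless of dosing delay".

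Section 9.1 places five PRO endpoints after OS and PFS in the confirmatory sequence. Section 9.4.2.1 assumes MAR for the MMRM (dyspnea, physical functioning, global health status), uses a cumulative-logit mixed model for chest pain and cough, and leaves further testing detail to the SAP. The SAP supplied is the integrated safety plan; it contains no PRO analysis.

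**The concern.** Discontinuation could mean the last dose or the decision to stop. The 6-weekly visits fall on dosing days in both arms. If the stop is decided there and the dose is not given, the last dose lies two to three weeks back. A last-dose cut-off would then discard the score from the stopping visit, and for a stop at week 6 that is the only post-baseline 6-weekly LC13 score.

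This matters for MAR. If subjects stop partly because of how they feel at that visit, keeping the score makes the stopping depend on observed data. Discarding it makes the same stopping depend on unobserved data.

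The two EOT timings seem to make things worse. On schedule, both can be met for tarlatamab but not for standard of care, so a cut-off of last dose plus 14 days would keep the score in one arm and lose it in the other. PRO claims that come up for testing would be at stake. OS and PFS would not.

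**Working it through.** The plan states no PRO sample size, SD or effect, so there is no figure of its own to reproduce.

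**1. Calendar.** Weeks 6, 12 and 18 from C1D1 are days 43, 85 and 127.
- Tarlatamab doses: 1, 8, 15, 29, 43, 57, 71, 85, 99, 113, 127. Gap to the previous dose: 43 − 29 = 85 − 71 = 127 − 113 = 14 days.
- Comparator cycles start on days 1, 22, 43, 64, 85, 106, 127. Before day 43, the last lurbinectedin dose is day 22 (gap 21), amrubicin day 24 (gap 19), topotecan day 26 (gap 17). Days 85 and 127 give the same gaps.
- With the ±7-day visit window the gaps become 7–21 (tarlatamab), 10–24 (topotecan), 12–26 (amrubicin) and 14–28 (lurbinectedin). The ranges overlap, and each contains gaps that meet the 14-day limit and gaps that miss it. The clean split by arm holds only on the nominal calendar.

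**2. Scores affected.** Assume exponential time on treatment with the protocol's pooled median of 4 to 6 months, S(t) = 0.5^(t/m), and every stop decided at a 6-weekly visit (t = 1.380, 2.760, 4.140 months).
- Missing under a last-dose cut-off, 1 − S at the visit: m = 4: 0.213, 0.380, 0.512 (mean 0.368); m = 6: 0.147, 0.273, 0.380 (mean 0.267).
- Missing under a decision-date cut-off, 1 − S at the previous visit: m = 4: 0, 0.213, 0.380 (mean 0.198); m = 6: 0, 0.147, 0.273 (mean 0.140).
- Difference, (1 − S₃)/3: 0.512/3 = 0.171 and 0.380/3 = 0.127. If only half the stops are decided at these visits, it is 0.085 and 0.063.

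**3. Bias in the arm difference.** Simulation of three visits analysed by likelihood under MAR. Assumed, not from the documents: SD 22, within-subject correlation 0.6, stop probability 0.15–0.30 per visit, log-odds of stopping up to 1.2 per SD worse score, and 250 per arm for error rates. Bias is averaged over weeks 6–18; positive means tarlatamab looks worse.

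| Scenario (no true effect; log-odds 0.7 unless stated) | Score kept in both arms | Score lost in both arms |
|---|---|---|
| Equal stop rates | −0.06 | −0.02 (error 5.2%) |
| 0.15 tarlatamab, 0.30 SOC | 0.04 | +2.42 (error 22%) |
| Same rates, log-odds 0.3 / 1.2 | 0.05 / 0.01 | +1.21 / +3.09 |
| 0.30 tarlatamab, 0.15 SOC | −0.02 | −2.39 (error 22%) |
| 0.15/0.30, stopping depends on earlier scores only | −0.04 | 0.02 |
| 0.15/0.30, stopping unrelated to scores | −0.05 | −0.03 |

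With the score kept, two-sided error is 4.8–4.9%. If it were kept for tarlatamab and lost for SOC, bias would be +3.7 points at equal stop rates (error 53%).

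**4. Which reading the text supports.** Sections 4.1, 8.1.3 and 8.1.4 use permanent discontinuation as the trigger for a visit and then count days from last dose. They treat the two as different things. Footnote c of the schema ties stopping to a decision. Scores taken *before or on* discontinuation naturally include one completed at the visit where treatment is stopped. No section sets the PRO cut-off at last dose or at last dose plus 14 days.

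**The case for a change.** The strongest opposing case is that the date is undefined for endpoints in a confirmatory sequence, that the wrong choice can raise the error rate to 22% or even 53%, and that a definition costs a sentence. The word *on* does not rule out the last-dose reading either, since forms on a dosing day are completed before the dose. The calendar gaps are correct, and the two EOT sentences do differ.

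That much stands, but it does not amount to a fault in the analysis.
- The error rates belong to cut-offs that appear nowhere in the plan. They also rest on a model in which stopping depends on the current score, so that keeping this score removes the bias by construction. The main reason to stop in Section 4.1 is radiographic progression, and in the SOC schedule the form is completed before the subject learns the disease status. Symptoms and progression may still be related, so dependence is possible, but its size is unknown.
- If the dose is given at the visit, the pre-dose score is kept under either reading.
- A long tarlatamab delay followed by a restart (Table 6-3: "Repeat tarlatamab step dose per cycle 1 guidelines") is not a discontinuation, so scores during it count.
- The EOT mismatch concerns a visit. The 6-weekly forms are scheduled from C1D1 regardless of dosing delay, so the mismatch does not decide whether they are collected.
- MAR is stated for the MMRM only, and a simulation with normal scores says little about the ordinal chest pain and cough models.
- Naming death in the estimand, delta-adjusted or while-alive analyses and completion tables are separate wishes, or questions for the study SAP.

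**Conclusion.** The concern does not call for a change. The protocol leaves the calendar date of discontinuation to the study SAP, and the ordinary reading of its wording keeps the stopping-visit score in both arms. Under that reading the simulated bias is within 0.06 points on an SD of 22, with error near 5%, provided stopping depends only on scores that are then observed.

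Under a last-dose cut-off the share of missing scores would rise by 13 to 17 percentage points on average (6 to 9 if half the stops are decided at 6-weekly visits). The arm difference would shift by about 0 to 3 points in either direction, and only with score-dependent stopping and an imbalance between arms. Neither condition is established.

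The schema footnote and Section 8.1.3 should be reconciled as a matter of wording. No view is taken here on which timing is right, and no test, model or alpha allocation turns on it. This conclusion rests on the study SAP not adopting a last-dose cut-off; anyone holding that document can check this directly.
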